### 8.1.2 Secondary Immunogenicity Endpoints

- The measures of immunogenicity of aQIV, aTIV-1 and aTIV-2 used for Secondary objective 1 as determined by the HI assay against homologous strains at Day 1 and 22 (unless indicated otherwise), include the following:
  - GMT: Geometric mean of HI titers on Day 1 and Day 22
  - Geometric mean ratio (GMR)\*: The geometric mean of the fold increase of post- vaccination HI titer over the pre-vaccination HI titer (Day 22/Day 1)
  - The percentage of subjects with a titer  $\geq 40$  at Day 1 and Day 22
  - SCR: the percentage of subjects with either a prevaccination HI titer  $< 1:10$  and a postvaccination HI titer  $\geq 1:40$  or a prevaccination titer  $\geq 1:10$  and a  $\geq 4$ -fold increase in postvaccination titer on Day 22
- For Secondary objective 2, the immunologic superiority of HI antibody responses for the alternate B strain (the influenza B strain included in the aQIV but not in the aTIV formulation) in aQIV will be assessed for each aTIV separately, using the endpoints of the ratio of HI GMT and the difference of SCR for each B virus strain 21 days after vaccination.

### 8.1.3 Secondary Safety Endpoints

Safety and tolerability will be assessed by the frequency and severity of:

- Solicited local and systemic adverse events (AEs) for 7 days following vaccination (Day 1 through Day 7)
- All unsolicited AEs for 21 days following vaccination (Day 1 through Day 22) and medication associated with these events
- Serious AEs (SAEs), AEs leading to withdrawal from the study, new onset of chronic diseases (NOCDs), AEs of special interest (AESIs), and concomitant medications associated with these events as collected from Day 1 through Day 181

### 8.1.4 Exploratory Immunogenicity Endpoints

- Exploratory immunogenicity endpoints include:
- GMTs: Geometric mean HI titers (GMTs) at Day 1 and Day 22
- SCRs: Percentage of subjects with either a prevaccination HI titer  $< 1:10$  and a postvaccination HI titer  $\geq 1:40$ , or a prevaccination titer  $\geq 1:10$  and a  $\geq 4$ -fold increase in postvaccination titer at Day 22.
- In case of any additional optional immunogenicity analyses, such as MN, or assessments using heterologous influenza strains, the immune response will be characterized in a similar manner as described in the secondary immunogenicity endpoints section above.

Further details regarding the endpoints and analyses of these assays will be described in the Statistical Analysis Plan (SAP) prior to unblinding.

## 8.2 Success Criteria

The study is considered successful if the co-primary objectives are achieved.

### 8.2.1 Success Criteria for Co-Primary Endpoints

#### 8.2.1.1 *To demonstrate noninferiority*

In line with the FDA Guidance on seasonal inactivated influenza vaccines (Guidance for Industry Clinical Data Needed to Support Licensure of Seasonal Inactivated Influenza Vaccines 2007), aQIV will be considered to be noninferior to aTIV-1, containing the same virus strains as the US licensed adjuvanted trivalent influenza vaccine, and aTIV-2, containing the alternate B strain if, for each of the four strains, the following statistical criteria are met:

- The upper bound of the two-sided 95% confidence interval (CI) for the ratio of the GMTs does not exceed 1.5. The GMT ratio will be calculated as  $\text{GMT}_{\text{aTIV}}/\text{GMT}_{\text{aQIV}}$ ; and
- The upper bound of the two-sided 95% CI for the difference between the SCRs does not exceed 10%. The difference in SCRs will be calculated as  $\text{Seroconversion}_{\text{aTIV}} - \text{Seroconversion}_{\text{aQIV}}$

### **8.2.1.2 CBER criteria for Co-Primary Endpoints:**

The endpoints for percent of subjects vaccinated with aQIV achieving seroconversion and HI titer  $\geq 1:40$  at Day 22 will be assessed against the criteria described in CBER Guidance Clinical Data Needed to Support the Licensure of Seasonal Inactivated Influenza Vaccines ([FDA, 2007](#)):

- The lower bound of the two-sided 95% confidence interval for the percentage of subjects achieving seroconversion for HI antibody should meet or exceed 30%
- The lower bound of the two-sided 95% confidence interval for the percentage of subjects achieving an HI antibody titer  $\geq 1:40$  should meet or exceed 60%

The statistical evaluation consists of the observed proportion together with the corresponding two-sided 95% CI per strain. No adjustment for type I error for multiplicity is made.

No adjustment for type I error for multiplicity will be made. The study is successful if the co-primary immunogenicity objectives are achieved.

### **8.2.2 Success Criteria for Secondary Objectives**

#### **8.2.2.1 Success Criteria for Secondary Immunogenicity Endpoints**

There are no specific success criteria for the assessment of immunoassay results (first secondary objective).

Superiority of aQIV versus aTIV-1 and aTIV-2 for the alternate B strain will be assessed using the GMT ratio ( $GMT_{aTIV}/GMT_{aQIV}$ ) and difference in SCR ( $SCR_{aTIV} - SCR_{aQIV}$ ) at Day 22. Point estimates and two-sided 95% CIs will be obtained as described for the primary endpoint. Superiority will be declared if the upper limit of the two-sided 95% CI for the difference in  $SCR_{aTIV} - SCR_{aQIV}$  is  $< 0\%$ , and the upper limit of the two-sided 95% CI for the GMT ratio ( $GMT_{aTIV}/GMT_{aQIV}$ ) is  $< 1$  for both B strains.

### **8.3 Description of Analysis Sets**

There will be four analysis populations defined for the study analyses. These are defined in more detail in the SAP.

#### **8.3.1 All Enrolled Set**

All screened subjects who provide informed consent, receive subject ID, and provide demographic and/or baseline screening information, regardless of the subject's randomization and treatment status in the study.

### **8.3.2 Full Analysis Set**

All subjects in the All Enrolled Set who are randomized and receive a study vaccination. The FAS will be used to produce summaries and listings of subject characteristics.

### **8.3.3 Safety Set**

The Safety Set will comprise all subjects in the FAS who received at least one dose or partial dose of Study Vaccine and have provided any evaluable follow-up safety data. The safety set will be used to produce summaries and listings of all safety data.

### **8.3.4 Evaluable Set – Immunogenicity Analysis**

The Evaluable Set for immunogenicity analyses will comprise all subjects in the FAS who:

- receive vaccine on Day 1
- provide serology specimens which yield valid serology assay results from both Day 1 and Day 22
- do not experience a laboratory-confirmed influenza illness between Day 1 and Day 22, and
- do not receive any prohibited medication during the study that is medically assessed to potentially impact immunogenicity results

### **8.3.5 Per-Protocol Set**

The Per-Protocol Set (PPS) will comprise all subjects in the Evaluable Set who do not have any protocol deviations that are medically assessed as potentially impacting on immunogenicity results.

The Per Protocol Set will be the primary population of interest for the primary/secondary immunogenicity analysis and a supporting analysis will be performed using the Evaluable Set. Membership of the PPS will be determined prior to unblinding the study.

Duplicate tables of primary and secondary immunogenicity analyses may also be produced based on the Evaluable population if there is >1% difference in the total number of subjects between the Per-Protocol Population and the Evaluable Population. The decision to produce tables based on the Evaluable Population will be made by Seqirus after population sets are finalised and prior to unblinding.

Examples for subjects excluded due to other reasons than protocol deviations are subjects who withdrew informed consent.

In case of misrandomization with regard to treatment arm, the subject is excluded from the PPS.

If a subject is unblinded during the study, except for SUSAR, he/she will be excluded from the PPS.

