### **3.2 Study Period**

Each subject should expect to participate in the study for approximately 6 months from the time of enrollment through the last study visit (Day 181 phone call).

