### **3.9 End of Study**

Evaluation of the primary and secondary immunogenicity objectives requires the testing of biological samples from the study subjects, which can only be completed after all samples are collected. The last samples for the analysis of the primary and secondary immunogenicity objectives will be taken at Day 22. For the purpose of this protocol, end of study is defined as the completion of the Last Subject Last Visit (LSLV), i.e. the last subject's Day 181 safety phone call, or the completion of testing of biological samples, to be achieved no later than 8 months after LSLV, whichever is longer.

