4.2 BLINDING AND UNBLINDING PROCEDURE

The trial is designed as a double-blind study. There are no visible differences between the investigational aQIV vaccine and the two comparator aTIV vaccines. Vaccines will be selected

and administered according to the Pack ID assigned to the subjects by IRT. Neither the subject nor any of the investigative staff who are involved in administering the vaccines or clinical evaluation of the subject will be aware of the vaccine administered.

In case of an emergency, the Investigator can determine the subject's assigned vaccine. The information can be retrieved from the IRT system either via web or phone (a 24/7 backup service).

Except in the case of medical necessity, a subject's treatment should not be unblinded without the approval of the Sponsor. In general, unblinding should only be performed when knowledge of the assigned treatment will affect a subject's management. In such instance of medical emergency, every effort should be made to contact the Sponsor prior to unblinding. If unblinding should occur (by either accidental unblinding or emergency unblinding for an SAE) prior to completion of the study, the Investigator must promptly contact the Sponsor and document the circumstances on the appropriate forms. Instructions regarding emergency unblinding will be provided to the Investigator.

All personnel involved in performing laboratory assays and others who are directly involved in the conduct of the trial or in the analysis of the final trial results will remain blinded to the treatment codes until at least the database has been locked for final analysis.

For details please refer to section 3.3 of the protocol.

If a subject is unblinded during the study, it is to be reported as major PD, except for subjects unblinded by Pharmacovigilance due to suspected unexpected serious adverse reactions (SUSAR). The unblinding will be documented appropriately (*for details see SOP on blinding*).

The unblinded subject(s) are excluded from the PPS. The unblinded subjects will be included in the FAS immunogenicity, and safety sets.

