6.1 Definition of Protocol Deviations

Major PDs are defined in accordance with International Conference on Harmonization (ICH) E3 as important PDs related to study inclusion or exclusion criteria, conduct of the trial, subject management or subject assessment resulting in the potential to jeopardize the safety or rights of the trial subjects or the scientific value of the trial. PDs will be classified as major and minor.

All PDs will be evaluated before unblinding and most will be classified into the following categories:

- Subject randomized and did not satisfy entry criteria
- Subject received the wrong treatment or incorrect dose
- Subject took an excluded concomitant medication
- Key study procedures missed or performed out of window

Major PDs will lead to exclusion of the subject or part of the subject's data from at least one analysis set.

The number of subjects in any and by PD category will be summarized by vaccine, center and overall. Individual subject listings will be provided in an appendix, sorted by subject and by PD category.

Prior to unblinding the analysis, designated Seqirus staff will develop a memo that describes the PDs that led to exclusions from analysis sets. This memo will be signed off by at least the Biostatistician and the Clinical Scientist and will be included in the trial master file (Exclusion Memo).

Prematurely terminating study participation for reasons such as withdrawal of consent or occurrence of AEs (including death) is not considered as a PD. Any missing assessments that

should have otherwise been collected for that subject later in the study is also not considered as a PD.

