7.4 Per Protocol Set (PPS) Immunogenicity

The Per-Protocol Set (PPS) will comprise all subjects in the FAS Immunogenicity who do not have any PDs that are medically assessed as potentially impacting on immunogenicity results.

The PPS will be the primary set of interest for the primary/secondary immunogenicity analysis and a supporting analysis will be performed using the FAS Immunogenicity. Membership of the PPS will be determined prior to unblinding the study.

Duplicate tables of primary and secondary immunogenicity analyses may also be produced based on the FAS Immunogenicity if there is >1% difference in the total number of subjects between the PPS and the FAS Immunogenicity. The decision to produce tables based on the FAS Immunogenicity will be made by Seqirus after analysis sets are finalised and prior to unblinding.

Examples for subjects excluded due to other reasons than PDs are subjects who withdrew informed consent, and subjects with RT-PCR-confirmed ILI prior to Day 22, as documented by the central laboratory.

In case of misrandomization with regard to treatment arm, the subject is excluded from the PPS.

If a subject is unblinded during the study, except for SUSAR, he/she will be excluded from the PPS.

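### The primary Per-Protocol Set has no Day 22 cut-off for consent withdrawal or unblinding, so subjects with complete endpoint data can be removed because of a later event

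*Protocol*

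**What the plan says.** The PPS is the primary set for the co-primary and secondary immunogenicity analyses (Protocol 8.3.5 and 8.4.2.2.2; SAP 7.4 and 11.1.3). In the protocol it is drawn from the Evaluable Set, whose members must "provide serology specimens which yield valid serology assay results from both Day 1 and Day 22". In the SAP it is drawn from the FAS Immunogenicity, which likewise needs data at both days (SAP 7.3).

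Two exclusions are then added:

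- **Consent.** Protocol 8.3.5: "Examples for subjects excluded due to other reasons than protocol deviations are subjects who withdrew informed consent". SAP 7.4 carries the same example. No date is attached.
- **Unblinding.** SAP 7.4, matching Protocol 8.3.5: "If a subject is unblinded during the study, except for SUSAR, he/she will be excluded from the PPS". The window is the whole study.

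On timing, Protocol 3.9 states: "The last samples for the analysis of the primary and secondary immunogenicity objectives will be taken at Day 22". Protocol 3.2 runs participation to the Day 181 telephone call.

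For the supporting analysis, Protocol 8.3.5 says "a supporting analysis will be performed using the Evaluable Set"; the SAP uses the FAS Immunogenicity for this. SAP 4.2 and 7.3 expressly keep unblinded subjects there. Neither document states a consent-withdrawal exclusion for that set.

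**The concern.** The co-primary endpoints are fixed by two blood samples, the later one at Day 22. Withdrawing consent or being unblinded months afterwards cannot change the antibody content of serum already drawn. Protocol 3.3 and 7.3 keep laboratory staff blinded, and 7.3 extends this to the visit. Yet either event can take the subject out of the set on which success is judged.

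Membership of the primary set then depends partly on what happens between Day 23 and Day 181, including safety events that lead to emergency unblinding. Such exclusions cost precision and serve no purpose that the documents state for immunogenicity. The undated wording also leaves those who finalise the sets to decide how a late withdrawal is treated.

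**Working it through.** **Step 1. Whom does the consent rule remove?**

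| Consent withdrawn | In the parent set? | Effect of the consent rule |
|---|---|---|
| Before the Day 22 sample | No: no valid Day 22 result | None; already out |
| After the Day 22 sample, by Day 181 | Yes, if both results are valid and the other conditions are met | Removed from the PPS |

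So the rule has work to do almost only for subjects who have given both samples.

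**Step 2. Does other text supply a cut-off?** In SAP 7.4 the neighbouring example, PCR-confirmed influenza-like illness, is limited to before Day 22. On a natural reading that limit does not reach the consent example in the same sentence. Protocol 8.3.7 mentions early termination as a non-deviation reason for excluding data, again without a date. No section limits either exclusion to events before the sample.

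**Step 3. Reproduce the plan's power.** Inputs from Protocol 8.5 and Table 8.5-1: one-sided alpha 0.025; seroconversion rate (SCR) margin 0.10; true SCR 0.73 (A strains) and 0.40 (B strains); GMT ratio margin 1.5; SD of the natural log titer 1.2; 800 aQIV and 400 per aTIV group, with the aTIV groups pooled for A strains.

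SCR power = Φ(0.10/√[p(1−p)(1/n₁+1/n₂)] − 1.96)

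- B strains: SE = √[0.24 × (1/800 + 1/400)] = 0.0300; Φ(3.333 − 1.96) = 91.5% (plan 91.29%).
- A strains: SE = √[0.1971 × (2/800)] = 0.0222; Φ(4.505 − 1.96) = 99.45% (plan 99.45%).
- Four SCR tests: 0.99454² × 0.91518² = 82.8% (plan 82.42%).

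GMT power = Φ(ln 1.5/[1.2√(1/n₁+1/n₂)] − 1.96)

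- B strains: Φ(0.4055/0.0735 − 1.96) = 99.98% (plan 99.98%). A strains: above 99.99%.
- All eight endpoints: 0.82843 × 0.99962 = 82.8% (plan 82.39%).

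The plan's figures are reproduced to within half a percentage point. The recruitment target also checks: 1600/0.9 = 1778.

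**Step 4. Remove an assumed share after Day 22.** The documents give no rate, so the shares below are assumptions, applied equally to all arms.

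| Share removed | Subjects of 1600 | aQIV / each aTIV | B-strain SCR power | Power, 8 NI endpoints |
|---|---|---|---|---|
| 0% | 0 | 800 / 400 | 91.5% | 82.8% |
| 1% | 16 | 792 / 396 | 91.3% | 82.3% |
| 2% | 32 | 784 / 392 | 91.0% | 81.7% |
| 3% | 48 | 776 / 388 | 90.7% | 81.2% |
| 5% | 80 | 760 / 380 | 90.1% | 80.0% |

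For the CBER criterion on B-strain titers of at least 1:40 (true rate 64.6%, threshold 60%), the normal approximation gives 76.2% with no loss (plan 76.47%), 75.8% at 1% and 74.0% at 5%.

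**The case against.** The other side has several good points.

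- **The data are not thrown away.** A reader might infer that they are. They leave the primary set but remain in the supporting set. This stands. It is not a full answer, because success is judged on the PPS. Both documents also promise a supporting analysis and then say duplicate tables may be produced if the sets differ by more than 1%, so what is guaranteed below that trigger is unclear.
- **Not everyone who is unblinded is excluded.** SUSAR cases are exempt in Protocol 8.3.5 and SAP 7.4. This stands.
- **No contradiction over protocol deviations.** SAP 6.1 says "Prematurely terminating study participation for reasons such as withdrawal of consent or occurrence of AEs (including death) is not considered as a PD", and it is tempting to set this against a PPS defined by deviations. But the consent example is introduced as a reason other than a deviation, and Protocol 8.3.7 allows such reasons. The passages agree.
- **No proven conflict over SUSAR.** SAP 4.2 closes with "The unblinded subject(s) are excluded from the PPS", which alone would cover SUSAR cases. The paragraph just before it exempts SUSAR unblinding from being a major deviation, and the closing sentence can be read as referring back to that. At most, an exception is not repeated.
- **The titer may not yet exist when consent is withdrawn.** Protocol 3.9 lets testing finish up to 8 months after the last subject's last visit. Leaving out a subject whose serum is untested can be a cautious choice. This stands, and the fix must provide for it. Protocol 3.8 stops further procedures after withdrawal, but does not say what becomes of samples already held.
- **No bias is shown.** The trial is double-blind and PPS membership is settled before unblinding. The documents give no reason to expect different losses between arms, so a claim of bias in a given direction would go beyond them.

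**Conclusion.** The point holds in a limited form. As written, the consent exclusion falls almost entirely on subjects with complete endpoint data, and the unblinding exclusion (SUSAR apart) can fall on them too. That a consent withdrawal as late as Day 181 would count is inferred from the missing time limit; for unblinding, the wording covers the whole study.

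The effect on power is small. Under an assumed 1% to 3% loss, spread equally over arms, power for the eight non-inferiority endpoints drops by about 0.5 to 1.7 percentage points and stays above the 80% target. At 5% it reaches that target. The 10% drop-out allowance may absorb such losses. These figures rest on the plan's own rates, normal approximations and independence between endpoints.

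The reason to act is therefore not power. It is that the set deciding success should not shrink for avoidable reasons arising after the endpoint, and that the rule should be clear before membership is settled. This is an inexpensive improvement; the trial's validity is not in doubt on this point.

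**What to change.** Before unblinding, amend Protocol 8.3.5 and SAP 7.4 and 4.2 as follows:

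1. Limit the consent exclusion to subjects who withdrew before the Day 22 blood sample.
2. Exclude a later withdrawal only if the subject also withdrew permission to use samples or data already collected, and say that this includes samples not yet tested.
3. Limit the unblinding exclusion to unblinding before the Day 22 blood sample, keeping the SUSAR exception.
4. Repeat the SUSAR exception in the closing sentence on the PPS in SAP 4.2.

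The cost is a few sentences. Protocol 5.5 puts the consent-withdrawal date on the termination CRF page for subjects who decline further follow-up, and Protocol 3.3 requires unblinding to be documented. The one item that may need adding is a record of whether permission to use collected material was withdrawn, since the documents do not describe one. SAP 14 already says the protocol will be updated to match the SAP's analysis-set language, so the wording can go into that revision.

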### 8.3.6 Subgroups

The immunogenicity analysis at Day 22 will be performed by stratifying for the following subgroups:

- Age at enrollment ( $\geq 65$ -74,  $\geq 75$ -84, and  $\geq 85$  years)
- Sex
- Race
- Previous influenza vaccination in the past 5 years (yes/no)
- Comorbidity/risk (yes/no, defined as assessment score  $< 50$  or  $\geq 50$  based on scale described in [Section 5.1.2](#) ([Hak, 2004](#))

Safety analysis of any unsolicited adverse events and of any local, any systemic, or any other solicited adverse events (all adverse events combined for each such category) will be performed by stratifying for the following subgroups:

- Age at enrollment ( $\geq 65$ -74,  $\geq 75$ -84, and  $\geq 85$  years)
- Sex
- Race

### 8.3.7 Protocol Deviations

A protocol deviation is any change, divergence, or departure from the study design or procedures of a study protocol. A protocol deviation may be a reason to remove data from an analysis set at the time of analysis. Major protocol deviations will be defined as exclusionary from the analysis according to protocol objectives and endpoints, which will be specified in the statistical analysis plan. In some cases, exclusion of data may be due to a reason other than a protocol deviation, e.g. early termination.

Any deviation that affects the subject's rights, safety, or well-being and/or the completeness, accuracy and reliability of the study data constitutes a major protocol deviation. Changes or alterations in the conduct of the trial which do not have a major

impact on the subject's rights, safety or well-being, or the completeness, accuracy and reliability of the study data are not considered major protocol deviations. All deviations will be reviewed to determine the final list of deviations that will be used for exclusion from the analysis set(s). This will be defined in the statistical analysis plan prior to unblinding.

All protocol deviations will be classified into those which are major and those which are not. Major protocol deviations will be summarized by vaccine, center (overall) and grouped into the different categories as defined above. The site monitor will keep the investigator informed of all protocol deviations, so that the investigator can comply with reporting these deviations to the local EC/IRB according to their institutional policy. Prior to unblinding, designated staff at the Sponsor will develop a memo that describes the selected deviations that are identified as exclusions from analysis populations. This memo will be included in the trial master file.

